**HADS** 

Connor Davidson Resilience Questionnaire

Self-efficacy using the Lorig self-efficacy questionnaire

Physical activity using the Duke Activity Status Index (DASI)

Each item is attributed a score from 1.75 to 8.0. If the answer is YES, the item score contributes to the total score. If NO, a score of 0 is added to the total score.

**MISSING**: 5 out of the 12 questions or less are reported, the DASI score would be considered missing or incomplete

Change in maximal inspiratory pressure (MIP)

Change in Spirometry (forced expiratory volume, FEV1 and forced vital capacity, FVC) measurements

= MIP on day of surgery – MIP at baseline

= Spirometry metric on day of surgery – spirometry metric at baseline

Mortality (in-hospital)

YES: Death recorded in hospital

NO: Participant was discharge from hospital

MISSING: otherwise

Mortality (to 30 days)

**YES:** Death recorded within 30-days following surgery

NO: Participant alive at 30-days following

surgery

Comprehensive Classification Index

MISSING: otherwise

Each Clavien-Dindo grade is assigned a weight. For instance, single complications are given weights as below:

Grade I: 8.7

Grade II: 20.9

Grade IIIa: 26.2

Grade IIIb: 33.1

Grade IVa: 42.1

• Grade IVb: 50.0

Grade V: 100.0

For multiples complications, the score is derived as the square root of the sum of all [(MRVphys × MRVpat)] and then divided by 2. This will provide a score between 0 and 100. The median (ratings are not normally distributed) reference value from physicians (MRVphys) and patients (MRVpat) for each grade are available at

http://links.lww.com/SLA/A405

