- vii)Data relating to the participant's surgery, ICU stay and hospital stay (including any PPCs and any other adverse events) collected in all participating patients;
- viii) Additional tests and medications (e.g. bronchodilators, antibiotics) prescribed for all participating patients during their hospital stay;
- ix) Data on MIP and spirometry at the end of the intervention (when patient is admitted for surgery);
- x) Data on PPCs, any other adverse events and health status questionnaires collected at 3 months and at 6 months post-surgery for all participating patients.

To minimise bias, all PPCs have been defined as far as possible on the basis of objective criteria (section 5.7.1). To minimise bias, outcome measures are defined as far as possible on the basis of objective criteria. All personnel carrying out outcome assessment (with the exception of MIP measurements) will be blinded; this will minimise detection bias. The data collection schedule is shown in Table 3.

We will track patients for mortality for 6 months after surgery using hospital tracking systems or centrally collected data (Office for National Statistics).

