#### Overview

Serious and other adverse events (AEs) will be recorded and reported in accordance with GCP guidelines and BTC (CTEU)'s Serious Adverse Events and Safety Reporting Standard Operating Procedure (SOP-GE-012) (see Figure 2).

[figure not shown]
INSPIRE Protocol Version 2.0 As there are no known long term safety concerns associated with using IMT, and any adverse events associated with IMT can only occur whilst the participant is undertaking IMT, safety reporting to the Sponsor will take place only while the participant is exposed to the intervention. In practice this means that the SAE reporting period will commence at the training session and continue until the patient is admitted to hospital for their index procedure. SAEs may be identified by ad hoc reporting from the patient, data collection at the extra training visits (where applicable) or on admission to hospital.

The complications or side effects of IMT, i.e. 'expected events' may include: dyspnoea, headache, pain, cough, nausea, chest discomfort, tachycardia, bradycardia, syncope, hypertension, bronchospasm, dizziness, syncope, epistaxis, respiratory distress, respiratory failure, perforated eardrum, cephalalgia. Any other event will be considered 'unexpected'. It is worth noting that the 'expected events' are events considered in other RCTs of IMT, but none of the RCTs have reported differences in the rate of any of these events between IMT/non-IMT groups, therefore these events may be regarded as hypothetical.

All unexpected and fatal SAEs will be reported to the coordinating centre, who will check the report and then forward to the Sponsor. Reporting to the Sponsor will occur within 24 hours of the site team becoming aware of the event. If the event is ongoing at the time of initial reporting the participant will be actively followed up and a follow-up report will be provided within 5 days of the initial report. Further follow up reports will be submitted only when there has been a significant change/update of the SAE until the SAE has resolved, or a decision for no further follow-up has been taken by the local PI.

All AEs during the participant's hospital stay and SAEs after hospital discharge will be recorded in detail on a CRF. At the conclusion of the study, all AEs recorded during the study will be subject to statistical analysis, and the analysis and subsequent conclusions will be included in the final study report.

Figure 2 Serious adverse event reporting flow chart

9.3

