#### 3.3 Analysis populations

#### 3.3.1 Intention-to-treat population

Analyses and summaries will be performed on an intention-to-treat basis. Analyses will use data from all participants randomised. The ITT population will consist of all randomised participants, included according to their randomised allocation, regardless of whether they are ineligible, prematurely discontinue treatment or are otherwise protocol deviators.

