## Statistical Analysis Plan Inspire IRAS Ref: 250345

Non-invasive ventilation (including continuous positive airway pressure (CPAP) and/or pressure support (BIPAP))

support (BIPAP))		
Optiflow (highflownasaloxygentherapy) Prophylactically to prevent a pulmonary complication	-	-
For treatment of a pulmonary complication	-	-
Length of ICU stay	-	-
Length of hospital stay	-	-
Antibiotic prescription	-	-
Bronchodilator prescription	-	-
Change in maximal inspiratory pressure (MIP)	-	-
Change in Spirometry (forced expiratory volume, FEV1 and forced vital capacity, FVC) measurements	-	-
Progression in training load		
In-hospital mortality	-	-
30-day mortality	-	-
Patient questionnaires at 3 months	-	-
Patient questionnaires at 6 months	-	-

\* Effect estimate is from model comparing high resistance IMT to the sham IMT and usual care groups combined

Table A12: PPC and progression in training load, within surgical specialty and ARISCAT score

Outcome	Randomised to IMT (n=xx)	Randomised to Sham IMT/Usual care (n=xx)
By surgical specialty		
Any PPC		
Cardiac (n=XXX)		
Non-cardiac (n=XXX)		
Progression in training load		
Cardiac (n=XXX)		
Non-cardiac (n=XXX)		
By ARISCAT score		
Any PPC		
Score 24-44 (n=XXX)		
Score ≥45 (n=XXX)		
Progression in training load		
Score 24-44 (n=XXX)		
Score ≥45 (n=XXX)		

Table A13: Adverse events and serious adverse events during index hospital admission

	Randor	mised Pa	tients (N=XXX	()		F	Relatedness (S	AEs)			Intensity (SAI	Es)
	AEs		SAEs							Una	anticipated eve	nts only
	Events/ Patients	% 	Events/ Patients	% 	Not related	Unlikely to be related	Possibly related	Probably related	Definitely related	Mild	Moderate	Severe
Any anticipated event												
Infective												
Viral Infection												
Pneumonia												
Respiratory infection												
Cardiovascular												
GI												
Respiratory/pulmonary												
Nervous system / Neurological / Psychiatric												
Immune system												
Metabolism / Nutrition												
Eye												

	Randor	nised Pa	tients (N=XXX	.)		R	elatedness (S	AEs)		Intensity (SAEs)		
	AEs		SAEs							Una	nticipated ever	nts only
	Events/ Patients	% 	Events/ Patients	% 	Not related	Unlikely to be related	Possibly related	Probably related	Definitely related	Mild	Moderate	Severe
Ear / Labyrinth												
Hepatobiliary												
Renal / Urinary												
Reproductive / Breast												

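### Out-of-hospital deaths before surgery or from day 31 to 6 months count in neither SAP mortality row, and any pre-surgery death shows as a non-death in the 30-day row

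*SAP*

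**What the plan says.** SAP 4.3.2 (Secondary outcome) defines two mortality variables.

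- **In-hospital:** YES is "Death recorded in hospital", NO is discharged, and anything else is MISSING. The rule names no admission, no link to surgery and no day limit.
- **To 30 days:** YES is "Death recorded within 30-days following surgery". NO is "Participant alive at 30-days following" surgery. Every other case falls under "MISSING: otherwise".

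Table A11 carries one row for in-hospital mortality and one labelled "30-day mortality". It has no row to 6 months and none counted from randomisation.

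The other relevant statements are these.

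- Protocol, Data collection: "We will track patients for mortality for 6 months after surgery", using hospital systems or national records. Protocol, Secondary outcomes lists mortality without a time point.
- SAP 1.1.2 keeps follow-up to 6 months after the early closure. SAP 2.3 names survival as something to be compared, again without a time point.
- SAP 3.3.1: "Analyses will use data from all participants randomised".
- SAP 4.2 takes percentages over the whole relevant population by default.
- SAP 4.4.3 limits secondary outcomes to tabulation. SAP 4.6 applies its missing-data strategy to the primary outcome alone and requires missing-data footnotes only for continuous variables.

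**The concern.** The 30-day clock starts at surgery, but participants enter the analysis at randomisation and train for at least two weeks before the operation. Someone who dies in that interval satisfies neither the YES nor the NO condition, so a known death is filed as missing data. This is also the exposure period: the protocol's safety section says that "any adverse events associated with IMT can only occur whilst the participant is undertaking IMT". At the other end, deaths after day 30 are ascertained for five further months, but no mortality variable is defined to receive them.

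At stake is whether the main outcome table shows how many randomised people died in each group. In a trial that closed early and will mostly be read descriptively, that count should be complete and correctly labelled.

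**Working it through.** No stated sample size, power or event count bears on this point, so there is no plan figure to reproduce. The check applies the two rules literally and then measures the windows. In the text as read from the PDF, the line closing the 30-day rule is displaced next to the following variable's label. I read it as belonging to the 30-day rule. Without it, a pre-surgery death would still be neither YES nor NO.

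**Step 1: coding by scenario**

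| Death | 30-day | In-hospital | Counted in either row? |
|---|---|---|---|
| Before surgery, outside hospital | MISSING | MISSING | No |
| Before surgery, in hospital | MISSING | YES | Yes (in-hospital) |
| Day 20, in hospital | YES | YES | Yes |
| Day 20, at home after discharge | YES | NO | Yes (30-day) |
| Day 45, still in index stay | NO | YES | Yes (in-hospital) |
| Day 100, at home after discharge | NO | NO | No |
| Day 100, in hospital on readmission | NO | YES if readmissions count, otherwise NO | Depends on the definition |

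The first and sixth scenarios fall through both rules. The last cannot be settled from the SAP.

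**Step 2: how a MISSING death is displayed**

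Let a group have n randomised, a deaths before surgery and b deaths from surgery to day 30. Under SAP 4.2 the 30-day row shows b/n, whereas the proportion of the group dying before surgery or by day 30 after it is (a + b)/n. The a deaths sit in the denominator and not in the numerator, so they read as non-deaths. Nothing in SAP 4.6 requires them to be footnoted or resolved. A participant who is alive but never operated on also falls to MISSING, so that category mixes deaths with survivors.

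**Step 3: share of time covered by the 30-day rule**

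- Taking 6 months as 180 to 183 days: 30/180 = 16.7% and 30/183 = 16.4%. The uncovered part is 150/180 = 83.3% to 153/183 = 83.6%.
- Adding the 14 to 56 days of training given in Protocol 6.4: 30/(180 + 14) = 15.5% and 30/(183 + 56) = 12.6%. The 56 days is not a ceiling, because training is extended when surgery is postponed.

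These are shares of calendar time, not of deaths. The documents give no mortality rate for the uncovered periods and no final number recruited.

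**Step 4: where else these deaths could appear**

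A fatal event is an SAE (Protocol 9.1), and SAEs are collected from the first training session to the end of 6-month follow-up (Protocol 9.3). SAP Table A15 covers SAEs throughout the trial. However, the SAE tables are arranged by body system and have no death row, Table A15 is absent from the output list that opens Appendix A, and SAP 3.3.3 groups the safety population by treatment received, not by randomised group.

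**The case against.** A fair defence has five parts.

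1. *The in-hospital rule catches some of these deaths.* This stands. A reader might infer that no death before surgery or after day 30 ever enters a mortality outcome. The text does not support that, because a hospital death before surgery and a late death in the index stay are both YES. The gap is confined to deaths outside hospital, plus readmission deaths if those are excluded.
2. *Deaths are reported elsewhere.* This largely stands. A reader might infer that the 6-month deaths are gathered and then withheld. The SAE tables, the participant flow diagram and the protocol's commitment, in its section on patient-reported outcomes, to report how many participants died all point the other way. What remains is that none of these is specified as a count of deaths by randomised group.
3. *The protocol left the time point open, and a surgical mortality measure is naturally anchored at surgery.* This is reasonable for choosing a 30-day measure, which also matches the primary outcome window. It does not explain coding a known death as MISSING, or having no variable for the tracked period. SAP 4.3.2 does use a 6-month window for antibiotic prescription.
4. *Nothing is tested.* This stands. Mortality has no effect estimate or p-value in Table A11, and the rows are labelled with their windows.
5. *The statements on survival and on the analysis population sit in SAP sections 1 to 3, which describe the original design, and the SAP follows protocol v3.0 whereas v2.0 is the version available.* This limits certainty. But section 4.5.2, written for the halted trial, still uses the ITT population, and SAP 1.1.2 retains 6-month follow-up.

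**Conclusion.** The coding rules should be corrected before analysis. As written, a pre-surgery death is MISSING for 30-day mortality and would be displayed as a non-death in that row. Out-of-hospital deaths before surgery, and from day 31 to 6 months, count in neither mortality row.

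The consequence is incomplete descriptive reporting of deaths by group. A reader might infer a biased treatment comparison; there is none to bias, because mortality is not modelled. The 30-day rule covers about 16% to 17% of the post-operative tracking window. It would be wrong to turn that into a number of deaths lost: the documents give no death rate outside the window, and the projected 321 Phase 1 participants belong to the original design.

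The conclusion assumes that the rules are applied literally, that the SAP 4.2 default denominator applies to Table A11, and that protocol v3.0 adds no mortality definition of its own.

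**What to change.** In SAP 4.3.2 and Table A11:

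- Add one descriptive row by randomised group for all-cause death from randomisation to 6 months after surgery. Split it into before surgery, surgery to day 30, and day 31 to 6 months. Code a pre-surgery death YES.
- For participants never operated on, count deaths from the SAE and follow-up data already collected, and give the number with unknown vital status. The protocol's mortality tracking is defined from surgery, so it does not by itself cover them.
- Restrict the existing 30-day row to participants operated on, and show that denominator.
- State whether in-hospital means the index admission only.

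The cost is some SAP wording and one table row. Post-operative deaths and fatal SAEs during training are already collected, and the row fits the tabulate-only plan. The SAP supplied is v0.3, and its revision section calls for sign-off of version 1.0 before any analysis, so that is the natural point for the change. The one drawback is that vital status may be incomplete for participants who never had surgery.

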#### **SWAT** primary outcome

The performance of IMT will be defined by the progression in training load from baseline.

## **SWAT** secondary outcomes

- Change in work (recorded on the IMT device) from baseline;
- Change in MIP from baseline;
- Change in spirometry markers (FEV1 and FVC) from baseline;
- Proportion of participants following at least 80% of the planned training sessions;
- Proportion of participants training at the prescribed intensity score of (RPE rating) ≥5

New variable	Rules
Change in load	

load on last line of patients diary – load at initial training visit

Change in work	

work in joules on last line of patients diary – work in joules at initial training visit

Change in MIP	= MIP on day of surgery – MIP at baseline
Change in spirometry markers (FEV 1 and	= FEV 1 on day of surgery – FEV 1 at baseline
FVC) from baseline	= FVC on day of surgery – FVC at baseline
Proportion of participants following at least 80% of the planned training sessions – recorded on patient diary	YES: If more than 22 (80% of planned 28) energy measurements are recorded on the patient diary
	NO: If 22 or less (80% of planned 28) energy measurements are recorded on the patient diary
	MISSING: otherwise
Proportion of participants following at least 80% of the planned training sessions – recorded on KHP2 device	YES: If more than 22 (80% of planned 28) energy measurements are recorded on the KHP2 device
	NO: If 22 or less (80% of planned 28) energy measurements are recorded on the KHP2 device
	MISSING: otherwise
Proportion of participants training at the prescribed intensity score of RPE rating ≥5	YES: If participant reported an RPE of 5 and above on their first, second and last line of patients diary
	NO: If participant reported at least one RPE below 5 on their first, second or last line of patients diary
	MISSING: otherwise
Proportion of participants training at the prescribed intensity score of RPE rating ≥5 – additional visit measurements	YES: If participant reported all RPE values of and above during the most recent 10 training sessions at their additional visit

(participants randomised to additional visit only)

**NO:** If participant reported at least one RPE below 5 during the most recent 10 training sessions at their additional visit

MISSING: otherwise

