#### 5.6.3.2 High resistance IMT training protocol

The mode of delivery of the high resistance IMT intervention in the main study will be contingent on the results of the SWAT with regards to the need for an additional face-to-face visit and manual vs. automatic load adjustment on the IMT device (section 5.2).

We will use a modified version of the IMT intervention protocol used in the recent study by Valkenet et al [23] (based on the protocol of Bailey et al [32]). Participants will undertake a maximum of 30 breaths (or as many breaths as can be tolerated), twice daily, 7 days per week, using the POWERbreathe® KHP2 at home. The initial training load for participants in the high intensity IMT arm will be set by the research nurse or physiotherapist at the first face-to-face meeting (section 5.6.3.1).

Training intensity will commence at 50% of MIP. If the patient cannot tolerate this, the load will be titrated to the maximum level that the patient can tolerate for at least 20 breaths (30 breaths is the maximum tolerable load) aiming for a starting workload of at least 40% of MIP. During the subsequent training intervention the load will be increased in accordance with tolerability quantified using rate of perceived exertion scale (a modified Borg exertion scale) which quantifies the perceived exertion of breathing from 0 to 10 ("How intense was the training session?") [30, 31]. Participants will refer to the RPE rating scale and rate their perceived exertion in their paper training diary after each training session.

Participants in Phase 1 who are randomised to the 'manual load adjustment' group will be given a table of pre-calculated training loads (Figure 3) to allow them to increase the load on their device by 5% if their perceived exertion at the end of a training session is 5 or less (using the RPE rating scale as shown in Figure 2).

Participants in Phase 1 who are randomised to the 'automatic load adjustment' group will be taught how to perform the first 3 test breaths using the IMT device which will automatically estimate MIP and adjust to the correct load. Participants in the 'automatic load adjustment' group will also record their perceived exertion using the RPE rating scale.

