# 6.4 Duration of treatment period

The duration of the treatment commences when the participant receives face to face training on breathing exercise regimens in all three arms; high resistance IMT, low resistance IMT or usual care. The duration of the breathing exercises will be for a minimum of two weeks before the day of surgery. In some instances the surgery date may be cancelled or postponed; in such instances, the duration of treatment will be extended further until an alternative surgery date is confirmed. For non-cancer surgery (e.g. elective heart surgery), the waiting time between referral for surgery and surgery may be longer than 2 weeks; therefore, participants will be recruited as soon as feasible and may be required to perform the intervention for up to 8 weeks before the day of surgery.

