#### SWAT primary outcome

The primary outcome of the SWAT will be the progression in training load from baseline. The secondary outcomes will be:

- Change in work (recorded on the IMT device) from baseline;
- · Change in MIP from baseline;
- Change in spirometry markers (FEV1 and FVC) from baseline;

- Proportion of participants following at least 80% of the planned training sessions;
- Proportion of participants training at the prescribed intensity score of (RPE rating ) ≥5.

We will consider removing the additional 'virtual' follow up meeting in Phase 2 if the increase in training load from baseline in the no additional 'virtual' follow up meeting group is similar to that in the additional 'virtual' follow up meeting group. We will consider automatic load adjustment in Phase 2 if the increase in training load from baseline in the automatic group is similar to that of the manual group. We will take into account any important interactions between the two interventions (loading method with or without an extra 'virtual' follow up meeting) when making the final decision regarding the delivery of the intervention in Phase 2.

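### The SWAT 80%-of-sessions outcome is scored against a fixed 28 with no counting window, although training may run well beyond two weeks

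*SAP*

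**What the plan says.** The SAP lists among the SWAT secondary outcomes the "Proportion of participants following at least 80% of the planned training sessions". The derivation table in SAP 4.3.2 turns this into two binary variables. The diary version is YES "If more than 22 (80% of planned 28) energy measurements are recorded on the patient diary". The device version is YES "If more than 22 (80% of planned 28) energy measurements are recorded on the KHP2 device". In both, 22 or fewer is NO. Neither rule says over what period the measurements are counted.

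Protocol 5.6.3.2 sets the frequency for high resistance IMT, the only arm in the SWAT, as "twice daily, 7 days per week". On length, Protocol 6.4 says: "The duration of the breathing exercises will be for a minimum of two weeks before the day of surgery". The same section says that participants awaiting non-cancer surgery "may be required to perform the intervention for up to 8 weeks before the day of surgery", and that treatment is extended when an operation is cancelled or postponed.

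SAP Table A8 lists training shorter than 2 weeks and longer than 8 weeks among the protocol deviations. A training period between those limits is therefore within protocol.

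**The concern.** The label promises a proportion of planned sessions, but the rule is a fixed count. Every recorded session enters the numerator, however long the participant trains, while the denominator stays at the two-week figure. Two participants with the same session-by-session behaviour can be classified differently only because one waited longer for surgery.

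At stake is what the reported percentage means. Readers of Table A10 will take it as the share of participants who did at least four-fifths of what they were asked to do. For anyone who trained longer than two weeks, it means only that they reached 23 sessions at some point. The error runs one way: whenever training lasts longer than two weeks, the fixed rule is easier to meet than a true 80% rule.

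**Working it through.** **Inputs**

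- Frequency: 2 sessions a day, 7 days a week, so 14 a week (Protocol 5.6.3.2).
- Length of training: at least 2 weeks and up to 8 weeks (Protocol 6.4; SAP Table A8 is consistent with this).
- Cut-off: more than 22, so at least 23 (SAP 4.3.2).

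**Reproducing the SAP's figure.** 2 × 7 × 2 = 28 sessions, and 0.80 × 28 = 22.4. The smallest whole number reaching 80% is 23 (23/28 = 82.1%; 22/28 = 78.6%). The cut-off is correct for a participant who trains for exactly two weeks.

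**Other lengths.** For w weeks:

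- prescribed sessions = 14w
- lowest share scored YES under the fixed rule = 23/(14w)
- sessions needed for 80% of the participant's own prescription = 0.8 × 14w, rounded up

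| Weeks | Prescribed | Lowest share scored YES | Needed for 80% |
|---|---|---|---|
| 2 | 28 | 82.1% | 23 |
| 3 | 42 | 54.8% | 34 |
| 4 | 56 | 41.1% | 45 |
| 5 | 70 | 32.9% | 56 |
| 6 | 84 | 27.4% | 68 |
| 7 | 98 | 23.5% | 79 |
| 8 | 112 | 20.5% | 90 |

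The fixed rule requires 23 in every row.

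**Illustration of misclassification.** Assume that sessions are independent and each is completed with probability 0.5. This is an assumption for illustration and is not in the documents. The probability of at least 23 sessions is then below 0.001 at 2 weeks, 0.32 at 3 weeks, 0.93 at 4 weeks and about 1.00 at 8 weeks. Under a cut-off scaled to the participant's own prescription it is about 0 at every length from 3 to 8 weeks.

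With a completion probability of 0.8, the fixed rule gives 0.50 at 2 weeks and about 1.00 from 3 weeks on. The scaled rule stays between 0.48 and 0.57 throughout. So the classification shifts with waiting time under the fixed rule but hardly at all under the scaled one.

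**The case against.** The best defence is that 28 was meant as a 14-day target. The Protocol's trial summary treats two weeks as the required dose, lets participants with a longer wait carry on if they wish, and speaks of monitoring training over the two weeks before the operation. Protocol 5.6.4.2 has similarly permissive wording for the low resistance arm. On that reading later sessions are optional, and 28 is the right denominator for everyone.

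Part of this stands. The documents differ on whether training beyond two weeks is prescribed or merely permitted, and the percentages in the table depend on treating it as prescribed. But the defence does not rescue the rule. A 14-day target needs a 14-day count, and SAP 4.3.2 counts all recorded measurements. A participant could reach 23 over several weeks and still be scored YES. On either reading the derivation has to change.

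It is also fair to say that the 21% figure is the extreme, that the cut-off is exactly right at two weeks, and that little hangs on the result. SAP 4.4.3 says SWAT secondary outcomes will be tabulated by factorial cell without modelling. SAP 1.1.2 records that the trial was closed at the end of Phase 1, so no Phase 2 delivery decision depends on it. The main adherence definition in the SAP is separate and is expressed per week. These points limit the consequences but do not make the rule correct.

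**Conclusion.** The rule is wrong as written for any participant who trains longer than two weeks. It is worth correcting before analysis, but the effect is confined to one tabulated SWAT secondary outcome in its diary and device versions. How many participants are misclassified cannot be said, because the documents give no waiting-time distribution. The conclusion assumes that Protocol 6.4 still applies: the protocol reviewed is version 2.0, while the SAP's page footer cites version 3.0. The 8-week limit in SAP Table A8 suggests that the range is unchanged.

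A reader might infer more than this, and the documents do not support it:

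- **That the outcome measures waiting time instead of adherence.** A long-waiting participant who does not train is still scored NO, and at two weeks the rule is exact.
- **That the SWAT primary outcome fails in the same way**, because change in load is "load on last line of patients diary – load at initial training visit". Load reached by the time of surgery is a legitimate target. SWAT cells are randomised within centre and specialty (Protocol 6.1), and models adjust for those factors (SAP 4.4.2), so unequal training time adds at most some noise. Large projected effects of duration on load do not survive the protocol's own limits: manual increases depend on perceived exertion being 5 or less, and automatic load follows estimated MIP.
- **That the result cannot be set beside the 54% completion figure cited in Protocol 2.4.** How that study defined its denominator is not given, so comparability can be neither affirmed nor denied.

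**What to change.** First reconcile the Protocol's trial summary, Protocol 6.4 and SAP 4.3.2 on what counts as planned sessions. This includes whether any two-week window runs from the start of training or back from surgery, since the trial summary suggests the latter. Then adopt one of two derivations:

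1. **Fixed window.** Count only sessions in the 14 days from the initial training visit, score YES if at least 23 of 28, and relabel the outcome so that the window is explicit. State how a participant operated on before day 14 is scored.
2. **Scaled denominator, where session dates are not held.** Use 2 × days from initial training to surgery as each participant's planned number, and score YES at 80% or more of it. Table A9 already plans days from randomisation to surgery; this option needs the date of the training visit instead.

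Apply the same rule to diary and device, and report total sessions and days trained descriptively by SWAT cell. The definition of the SWAT primary outcome does not need to change.

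The cost is a re-derivation and a changed label, with no change to what participants do. SAP section 7 provides for documented changes before analysis begins. Option 1 needs dated sessions, and the documents do not confirm that these are held; under it, sessions after day 14 no longer count in this binary outcome, which is why the totals should be shown alongside.
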